1.1 STUDY OBJECTIVE

PulmoVista 500 is a lung function monitor for clinical use which continuously generates cross-sectional images of the lung function by applying the technique of electrical impedance tomography (EIT).

To perform bioimpedance measurements, an electrode belt containing 16 electrodes is placed around the chest wall. Additionally, one reference electrode must be attached to a central point to the body, preferable on the abdomen. The reference electrode ensures that all measurements at different electrode pairs are referenced to the same electric potential¹. PulmoVista 500 provides graphical information about the regional distribution of ventilation and changes of end-expiratory lung volume. The spatial resolution of this information allows continuously observing specific conditions of different lung regions.

The primary objective of this study is to assess the capability of PulmoVista 500 to continuously monitor ventilation and changes of lung volume

For this propose cross-correlations between the global impedance waveforms created by a ventilator shall be evaluated.

1.2 STUDY DESIGN

The study is a multicenter, prospective, non-interventional, and open observation study. The clinical trial will be conducted according to the German Medical Device Act as §23b clinical trial and in compliance with the ISO 14155.

1.3 DEFINITIONS

The intention-to-treat collective comprises all patients for which both, the impedance waveforms and parallel to them volume waveforms have been generated during ventilation. If one of the two waveforms has not been created or cannot be evaluated, the patient is considered as drop out.

A waveform is not generated if

- a) it has not been recorded correctly, so all the individual values are zero or
- b) there is no complete 1-minute file before the "PRE" marker or behind the "POST" marker available for the statistical calculation of the cross-correlation coefficient.

¹ Teschner E, Imhoff M, Leonhardt S. Electrical Impedance Tomography: The realisation of regional ventilation monitoring. Drägerwerk AG & Co. KGaA 2015; Reference-Nbr 90 66 788;

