7 STATISTICAL CONSIDERATIONS

7.1 SAMPLE SIZE, DROP-OUT-RATES, LEVEL OF SIGNIFICANCE AND POWER OF THE CLINICAL INVESTIGATION

Primary Endpoint (Efficacy)

Based on former porcine trials⁷ with PulmoVista 500 and data from clinical studies with other EIT devices the sample size was calculated using the program G*Power 3.1.9.2.

An α -error of $p = 0.05$ and a power = 0.9 in a two-sided testing resulted in a sample size of 68 patients. With this sample size a difference of 0.1 of the mean cross-correlation coefficient shall be detected, i.e. the true value of a calculated mean of 0.8 will not be smaller than 0.7 and not be larger than 0.9 with the given p-value and power under the assumption of a standard deviation of less than .25.

Accounting for 15 % potential drop-outs 80 patients shall be enrolled in the study.

Secondary Endpoint (Efficacy)

Based on former porcine trials with PulmoVista 500 and data from clinical studies with other EIT devices the sample size was calculated using the program G*Power 3.1.9.2. An α -error of $p = 0.05$ and a power = 0.9 in a two-sided testing resulted in a sample size of 22 patients. With this sample size a difference of 0.1 of the proportion between reference and investigated variable shall be detected.

Accounting for 15 % potential drop-outs 25 patients shall be enrolled in this subgroup of the study.

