7.2 STATISTICAL DESIGN

Null-Hypothesis

The PulmoVista 500 is not capable of continuously monitoring ventilation.

Primary Endpoint (Efficacy)

To assess the capability of PulmoVista 500 for continuous monitoring of ventilation and its changes at different points in time during varying states of regional ventilation, the cross-correlation function (CCF) between global tidal impedance (EIT) waveforms and global tidal volume (ventilator) curves will be evaluated.

- To refute the null-hypothesis of this trial it must be shown that the global tidal impedance waveforms and the global tidal volume curves correlate

⁷ Fischer E, Gremse F. Assessment of the capability of PulmoVista® 500 to continuously monitor regional ventilation distribution and its changes over time. An Animal Study. FINAL STUDY REPORT. PulmoVista 500-30022. Aix Scientifics. 2016-01-27

significantly, i.e. that the correlation scores are significantly different from zero.

- If the null-hypothesis is refuted the capability of PulmoVista 500 is assumed to be a valuable diagnostic device for long-term monitoring of mechanical ventilation.

The mean value of the intra-subject cross-correlation function (CCF) between global impedance (EIT) waveforms and global volume (ventilator) curves will be determined.

Secondary Endpoint (Efficacy)

To assess the capability of PulmoVista 500 to detect regional changes of ventilation it shall be tested, whether EIT can correctly differentiate between normal and single-lung ventilation.

- To refute the null-hypothesis of this trial it must be shown that the regional information about tidal impedance variation matches the clinical changes from normal to single-lung ventilation, i.e. that EIT detects ventilation vs. no ventilation in each lung.
- If the null-hypothesis is refuted the capability of PulmoVista 500 is assumed to be a valuable diagnostic device for detecting regional ventilation changes during long-term monitoring of mechanical ventilation.

The diagnostic output of the EIT measurements will be compared with clinical ventilation settings in a 2x2 table.

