7.8 PROCEDURES THAT TAKE INTO ACCOUNT ALL DATA

The Full Analysis Set (FAS) consists of all enrolled patients. This excludes non-informative drop-outs. A per protocol analysis may be specified in the statistical analysis plan excluding major protocol violations.

Safety Analysis Population (SAP) consists of all enrolled patients who already were treated with the medical device (PulmoVista 500).

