4 TREATMENT OF MISSING, UNUSED OR SPURIOUS DATA, INCLUDING DROP OUTS AND WITHDRAWALS

4.1 MISSING VALUES

No missing data imputation techniques will be applied, and patients with missing efficacy data will be used as censored in the time to event analysis. Therefore any effort should be undertaken to avoid missing data, notably in case of the primary outcome measures.

When a patient is withdrawn from the trial before the scheduled end of a treatment phase, and an end-of-study visit can be performed, the data of this visit will be used for computing the primary outcome measure.

The handling of missing data will be specified in the Data Review Meeting.

Only data from patients for whom appropriate ventilation waveforms are available can be evaluated. Patients without evaluable ventilation waveforms are drop-outs.

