5.6 SECUNDARY ANALYSIS

5.6.1 Efficacy

- To demonstrate the ability of PulmoVista 500 to visualize regional ventilation changes, a quantitative evaluation is performed by calculating the cross-correlation coefficients between the impedance waveforms of PulmoVista 500 and the ventilator volume waveforms of OLV patients. The evaluation is carried out as in the primary analysis.
- In addition, a qualitative evaluation of the regional changes will be carried out. To do so, three blinded raters compare the corresponding sections of all OLV patients independently. Based on the information from the PulmoVista 500 video sequence provided, the raters evaluate which of the two halves of the lung is ventilated. The results are entered patient-related (pseudo-patient number) in the following table by the rater:

Pseudo-Patnr.	Valuation	
1	1	
2	2	
3	0	
4	1	
.	.	

Description of valuation:	0	not assessable
	1	right ventilated / left blocked
	2	left ventilated / right blocked

Tab. 1: Example of table for the qualitative evaluation of the OLV patients and the associated rating

The PulmoVista 500 video sequences to be assessed are created according to a workflow (see Appendix 7.3 Workflow for the creation of OLV videos) and made available to the raters. The pseudo-patient numbers are randomly generated by lot. These three tables of the raters will be merged into the KKS. A decision is considered positive or negative if at least two raters have come to the same result. In the opinion of one or more raters, is it not possible to judge the waveform (Code 0), the following assignment applies:

1x not evaluable & 2x same decision -> clear assignment in the table,
 1x not assessable & unequal decision of the remaining 2 raters -> drop out,
 2x or 3x not evaluable -> drop out.

A 2x2 Table will be created in the following form from the 3 tables of the raters (one of each rater):

Reference	Evaluation of the raters (with information provided by PulmoVista 500)	
	right ventilated / left blocked	left ventilated / right blocked
right ventilated / left blocked	a	b
left ventilated / right blocked	c	d

Tab. 2: Table for the accordance of rater and reality of the OLV patients

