From this table, the success rate $(a + d) / (a + b + c + d)$, the sensitivity $a / (a + b)$, the specificity $d / (c + d)$ and the corresponding confidence intervals are calculated. The reverence (real side of the ventilation) is taken in the study documentation (e.g. Name of corresponding Marker and/or MACRO Database) of the individual patients.

- To assess the ability of PulmoVista 500 to display changes in ventilation-induced tidal volumes through the "Trend View", the plausibility questionnaire across all patients is evaluated. The questions of the plausibility questionnaire in relation to the "main view" are individually counted according to their categories (yes / no / n.a.) and listed as a percentage.
- To assess the ability of PulmoVista 500 to display changes in end-expiratory lung volumes (induced by e.g. PEEP changes, recruitment and suction maneuvers) using the "dELLI Trend View", the plausibility questionnaire is evaluated across all patients. The questions of the plausibility questionnaire in relation to the "dELLI trend view" are individually counted according to their categories (yes / no / n.a.) and listed as a percentage.
- The evaluation of clinical usefulness, the nine questions of the questionnaire on clinical usefulness, are individually counted according to their category level (1 very difficult ... to ... 5 very useful) and listed on a percentage basis. Furthermore, the mean and standard deviation are calculated for each of these nine questions.

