7 APPENDIX

7.1 REFERENCE VALUES OF LABORATORY PARAMETERS

[figure not shown]
Omitted

7.2 WORKFLOW FOR DETERMINING THE TIME RANGES USED TO CALCULATE THE CROSS CORRELATION BETWEEN THE GLOBAL IMPEDANCE WAVEFORM (PULMOVISTA 500) AND THE VOLUMETRIC WAVEFORM (EVITA V500).

Workflow for determining the time ranges used to calculate the cross correlation between the global impedance waveform (PULMO VISTA 500) and the volume waveform (EVITA V500)

[figure not shown]
Step Description

- 1 Open EIT Data Analysis Tool SW 6.1
- 2 Use the **Load** button to load the first file in the series containing the intervention to be evaluated; the beginning and the type of intervention are marked by an event marker (see example below)
- 3 Use the button **Sequence to ...** to load the last file of the series containing the intervention to be evaluated
- 4 Record the total length of the loaded files (time scale below ROI 4)

[figure not shown]
5 Select the files (1 min each) that lie directly before (1) or after (2) the intervention, in which a uniform impedance waveform, and in particular no artifacts, can be seen and in which no parts of the intervention itself are contained.

Example: series of 10 files per 1 min, in which the interventions took place between min 3 and 4.

[figure not shown]

6 Place cursor in the area of file 1 (exact position does not matter, in this example within the third minute)

- 7 Use the buttons **Display ...**, **Time scale** to set the time scale to 60 sec

- 8 Use the button **File ..., save as ASC** to convert the selected file 1 as ASCII file
(the created ASC file is saved in the same directory with the same file name as the selected EIT file, and a two-digit, incremental counter is added to the file name)
- 9 Use the Buttons **Display ...**, **Time scale** to increase the time scale so that the recorded total length is displayed again.
- 10 Place cursor in the area of file 2 (exact position does not matter, in this example within the 5th minute)
- 11 Use the buttons **Display ...**, **Time scale** to set the time scale to 60 sec

- 12 Use the button **File ..., Save as ASC** to convert the selected file 2 as ASCII file
- 13 Now open the two generated ASC files with the statistical evaluation software
- 14 In the area below the line (Image; Time; Global;), Determine the cross-correlation between column C (Global) and column N (~ Volume [ml]).

97	A	B	C	D	E	F	G	H	I	J	K	L	M	N

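### The one-lung-ventilation success rate leaves out clips the raters could not read, and the SAP plans no count, by cause, of patients lost to an unusable EIT signal

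*SAP*

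**What the plan says.** **OLV rating.** Protocol 7.2 sets the regional criterion as showing "that EIT detects ventilation vs. no ventilation in each lung". SAP 5.6.1 has three blinded raters code each OLV patient's clip as right ventilated, left ventilated or not assessable (code 0). Two agreeing raters decide. A clip is a drop-out if it is "2x or 3x not evaluable", or if one rater gives code 0 and the other two disagree. The success rate is then (a+d)/(a+b+c+d), taken from a 2x2 table (Tab. 2) with no cell for dropped clips.

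**CCF set.** SAP 1.3 defines the intention-to-treat collective as patients with both an impedance and a volume waveform, and adds: "If one of the two waveforms has not been created or cannot be evaluated, the patient is considered as drop out". A waveform counts as not generated if all its values are zero or if a complete one-minute file is lacking. SAP 4.1 repeats the rule: "Patients without evaluable ventilation waveforms are drop-outs". The further collectives in SAP 1.4 (undisturbed) and 4.2 (without outliers) are narrower than this set.

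**Protocol set.** Protocol 7.8 starts from all enrolled patients and says: "This excludes non-informative drop-outs". The SAP plans no analysis on that set.

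**Choice of minute.** SAP 7.2, step 5, selects one-minute files next to the intervention "in which a uniform impedance waveform, and in particular no artifacts, can be seen".

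**The concern.** For a question about device capability, an unreadable EIT display is not a neutral missing value. A clip from which raters cannot tell the ventilated side does not meet the criterion in protocol 7.2. An all-zero impedance trace is not evidence of monitoring. An exclusion caused by EIT failure is therefore informative, whereas protocol 7.8 removes only non-informative drop-outs.

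Protocol 7.3 defines no pass/fail criterion, so readers will judge the device on the success rate, the mean CCF and their intervals. If unreadable recordings leave both results uncounted, and the set is labelled intention-to-treat, a reader cannot tell performance in all measured patients from performance in those whose signal was usable.

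**Working it through.** **1. The plan's own figures.** Protocol 7.1: difference 0.1, SD 0.25, two-sided alpha 0.05, power 0.90. A one-sample t-test with standardised effect 0.1/0.25 = 0.4 gives n = 68 (power 0.902), and 68/0.85 = 80. Both figures reproduce, and the allowance is 80 - 68 = 12 patients for all causes.

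For OLV the protocol states 22 evaluable patients and says "25 patients shall be enrolled in this subgroup of the study". The 22 reproduces only if the reference proportion is about 1 (1 - 0.9^22 = 0.9015). 22/0.85 = 25.9, so 25 is one short of full inflation, which does not matter here. The allowance is 25 - 22 = 3 patients.

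**2. Which OLV clips are dropped.** There are two sides and three raters.

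| Code-0 ratings | Remaining ratings | Result |
|---|---|---|
| 0 | three readable | always a majority, kept |
| 1 | two agree | kept |
| 1 | two disagree | dropped |
| 2 or 3 | one or none | dropped |

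Every drop-out under this rule involves at least one not-assessable rating.

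**3. Direction.** Let u be the number of unreadable clips or recordings. Since u is at least 0, (a+d)/(a+b+c+d+u) is never larger than (a+d)/(a+b+c+d). The planned rate is therefore an upper bound on the rate that counts unreadable clips as not correct.

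**4. Size for OLV.** Assume all 22 assessable clips are rated correctly, and that of the other three patients u were unreadable on EIT while the rest were lost to marker, video or care-related causes. Clopper-Pearson 95% intervals:

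| u | Planned rate | Rate counting u |
|---|---|---|
| 0 | 22/22 = 100% (84.6 to 100) | 22/22 = 100% (84.6 to 100) |
| 1 | 22/22 = 100% (84.6 to 100) | 22/23 = 95.7% (78.1 to 99.9) |
| 2 | 22/22 = 100% (84.6 to 100) | 22/24 = 91.7% (73.0 to 99.0) |
| 3 | 22/22 = 100% (84.6 to 100) | 22/25 = 88.0% (68.8 to 97.5) |

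The planned result is the same in all four rows.

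**5. The CCF test.** As an extreme check of the test only, take the planning mean 0.80 and SD 0.25 in 68 patients, and score all 12 allowed drop-outs as 0. An all-zero series has no defined correlation, so this score is a convention.

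- Mean: 68 x 0.80/80 = 0.68.
- Sum of squares: 67 x 0.25^2 + 68 x 0.12^2 + 12 x 0.68^2 = 10.72.
- SD: sqrt(10.72/79) = 0.368.
- t = 0.68/(0.368/sqrt(80)) = 16.5, against 0.80/(0.25/sqrt(68)) = 26.4 in the 68 evaluable patients.

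Rejection of zero correlation does not depend on the exclusions. The documents give no failure count, so no size can be put on bias in the mean.

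**The case against.** **Evaluable-patient analysis was planned.** Protocol 7.1 allows for drop-outs, and such an analysis is not itself an error. That stands. What is missing is a count of EIT failures beside it and an accurate label.

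**Other planned outputs touch the question.** Plausibility question 2 (protocol 23.2) asks whether the Tidal Image shows the correct unventilated side while one lung is blocked. SAP 5.6.1 tabulates the main-view answers as yes, no or n.a. SAP 3.1 and 5.2 present signal quality by its distribution. It would therefore be wrong to say that nothing planned bears on unusable signals. But the questionnaire is optional and unblinded, and neither output counts unusable recordings or enters the two estimates. The device-deficiency records of protocol 16.1 are not linked to them either. The raw cells of Tab. 2 would reveal a shortfall from the enrolled number, but not its cause.

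**Not every exclusion is a device failure.** This stands. The missing-file criterion in SAP 1.3 is logistical, ventilator failures are removed by the same rule, and SAP 1.3 does not remove a patient merely for a disturbed signal. Checks before recording (protocol 6.4.2) and staff at the bedside (protocol 6.1.2) may keep EIT failures few. The undefined part is what makes a waveform impossible to evaluate.

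**Step 5 may be consistent with 1.4 and 4.2.** A reader might infer a contradiction, because step 5 already screens out artifacts while the undisturbed sets are described as additional. The text does not force that reading: step 5 chooses a minute within a patient, whereas 1.4 and 4.2 define sets for additional evaluation. The relation is unstated, not contradictory.

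**Conclusion.** The point holds, most firmly for the OLV success rate. There the direction is certain and follows from the SAP's own rules. The size depends on how many clips are unreadable on EIT. Within the protocol's allowance of three, and with every assessable clip correct, the rate counting them ranges from 100% down to 88.0%, while the planned rate stays at 100%. The 88.0% assumes that all three losses are EIT failures; it is not a forecast.

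For the CCF the supported statement is weaker. A set called intention-to-treat omits patients with an unusable impedance waveform, no count by cause is planned, and the mean may be biased upward by an unknown amount. A reader might infer that the mean is overstated by 0.80 - 0.68 = 0.12, or that the primary test is undermined. The documents support neither. The 0.12 needs every allowed drop-out to be an EIT failure and a zero score that the plan does not contain, and the t-test against zero is unaffected even then. The matter should be fixed in the SAP before data review; it concerns estimates and labelling, not rejection of the null hypothesis.

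**What to change.** 1. **SAP 5.6.1, Tab. 2.** Add a not-assessable column with cells e and f by reference side, and a cell g for OLV patients who had the device applied but have no usable EIT recording and no documented side. Beside the current versions, report (a+d)/(a+b+c+d+e+f+g), a/(a+b+e) and d/(c+d+f) with confidence intervals, and give the count e+f+g. List separately the losses from documented marker or video errors, or from recording stopped for medical care.

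2. **SAP 1.3.** Call the set evaluable, define when a waveform cannot be evaluated, and tabulate exclusions by cause (EIT, ventilator, marker, care-related) among all patients with the device applied. A sensitivity analysis scoring EIT-only failures as CCF = 0 is optional. If used, label it a convention and a named exception to the no-imputation rule.

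3. **SAP 7.2, step 5.** State how visual selection of artifact-free minutes relates to the additional sets in 1.4 and 4.2. As a sensitivity analysis, report the CCF from the nearest complete minute that contains no part of the intervention, without artifact screening.

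**Cost.** SAP wording and no new patient measurements. A cause must be assigned to each exclusion, for example in the Data Review Meeting; no specified field now separates EIT, ventilator and marker causes. Up to 80 x 2 = 160 one-minute files need checking, and those where the screened minute is not the nearest must be re-extracted. Reported estimates may be slightly lower.

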1.4 APPLICATIONS

The primary efficacy analysis is performed on the Intention-to-treat collective. Additionally a collective will be evaluated in which the impedance waveforms are probable without external disturbances. The decision about his patient classification will be done in the Data Review Meeting.

1.5 PATIENTS

The following patients will be enrolled:

a) Intensive care unit (ICU) patients, who are mechanically ventilated via an artificial airway (endotracheal tube or tracheostomy cannula) and who are expected to be subjected to major changes in their ventilator settings will be monitored with the PulmoVista 500 device before, during and after the changes.

Examples of such interventions are:

- Spontaneous breathing trial (SBT) using the ventilator (as opposed to SBT using a T-piece)
- Switching between different modes of ventilation (e.g. volume controlled, pressure controlled, pressure support, CPAP)
- Initial adjustment of ventilation after ICU admission
- Weaning of ventilation in preparation of extubation
- PEEP trials and recruitment maneuvers
- Suctioning maneuvers

b) One lung ventilation (OLV) patients who are scheduled for planned surgical procedures requiring ventilation of only one lung wing (e.g. DLT- intubation using a double lung tube or placement of a bronchus blocker).

1.6 SERIOUS PROTOCOL VIOLATIONS

Serious protocol violations are documented. In the Data Review Meeting, the classification of patients with serious protocol violations is decided. The data review meeting takes place after completion of the data input and the data correction (answering all queries). Participants are usually coordinating investigator or his representative, a representative of the sponsor, the data manager, the study manager / monitor and the biometrics.

